11.4 Confidentiality

Subject records will be kept in a secure location at Stanford University Medical Center, accessible only to research authorized personnel. The subject identity will be kept as confidential as possible as required by law. Except as required by law, the subject will not be identified by name, social security number, address, telephone number, or any other direct personal identifier. Study subjects will be assigned an ID code that will consist of a three digit number. Information about the code will be kept in a secure location and access limited to research study personnel. The results of this research study may be presented at scientific or

medical meetings or published in scientific journals. However, the subject identity will not be disclosed. The subject's personal data which may be included in the investigator's database shall be treated in compliance with all applicable laws and regulations.

12. STATISTICAL CONSIDERATIONS

12.1 Statistical Design

The phase 1B portion of this trial is designed to allow preliminary assessments of safety and biological activity. No pre-specified hypothesis testing will be performed.

The phase 2 portion of this trial will be powered to detect an improvement in response equal to the combined overall response rate of each intervention alone (SD-101 and ibrutinib)

12.2 Primary Analysis

12.2.1 Analysis Population

Phase 1B – Safety

The safety population will consist of all enrolled subjects who received at least one dose of any study treatment. The safety population will be used for the analysis of safety data.

Phase 2 – Efficacy

The response-evaluable population is defined as all enrolled subjects who received at least one dose of study treatment (ibrutinib or SD-101) and provided at least one post-baseline response (or disease) assessment. The response-evaluable population will be used as the primary population for analyses based on overall response.

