SECONDARY OBJECTIVE(S)	
Phase 2:
 
1) To evaluate progression-free survival after treatment with intratumoral SD-101 in combination with ibrutinib and radiation in subjects with relapsed or refractory B-cell lymphoma2) To evaluate the induction of tumor-specific immune responses by treatment with intratumoral SD-101 in combination with ibrutinib and radiation in patients with relapsed or refractory B-cell lymphoma

TREATMENT SUMMARY	
Local low-dose radiation therapy to a single site of disease combined with intratumoral injections to the same single site.
 
SD-101 (CpG) – Intratumoral injection on Day 2, then once every week x 4 successive weeks for a total of 5 injections at a dose of 3 mg per dose in cohort 1 or 1 mg per dose in cohort -1.
 
Ibrutinib orally at a dose of 560 mg daily starting on Day 10 until progression of disease or for 96 weeks, whichever comes first.
 
In the safety portion of the study, a starting dose of 3 mg SD-101 and 560 mg ibrutinib will be studied and will follow a 6+3 dose de-escalation design. In the first cohort of 6 subjects, if ≤ 1 subjects experiences a DLT, then that dose level will be chosen as the recommended phase 2 dose. If 2 subjects experience a DLT, then an additional 3 subjects will be enrolled at the same dose level. If 3 or more of 6 to 9 subjects experience a DLT, dose de-escalation will occur with a new cohort of 6 subjects at a dose of 1 mg SD-101 and 560 mg ibrutinib.
 
Based on the data from dose de-escalation cohorts, a dose of SD-101 will be chosen and an additional cohort of 15 subjects will be treated at that dose in order to assess the clinical response rate.
 
Immune monitoring and follow-up will occur over the following 24 weeks.
 
Subjects without PD will be followed for immune and clinical response every 12 weeks until Week 96 or progression, whichever comes first.

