4. TREATMENT PLAN

4.1 Dose de-escalation Study Design

The study will use a 6+3 design with a goal of determining the recommended phase 2 dose. We will enroll a cohort of 6 subjects, with a 3 mg dose of intratumoral SD-101 and 560 mg dose of oral ibrutinib. The proposed initial dose of SD-101 is below the maximum tolerated dose as determined in previous trials, and there is extensive data regarding the safety of treatment with ibrutinib at the FDA-approved dose of 560 mg. Because no additional toxicity is anticipated with combination therapy of SD-101 and ibrutinib, the 6+3 dose de-escalation design will be employed, permitting rapid confirmation of the safety of the combination therapy and selection of the recommended phase 2 dose while still allowing detection of any unanticipated toxicity.

If 0 or 1 subjects out of the initial 6 subjects experience a DLT, we will chose this dosing as the recommended phase 2 dose level. If 2 out of 6 subjects experience a DLT, we will expand the

cohort and enroll an additional 3 subjects at the same dose level. If 3 out of 6-9 subjects in the initial dose cohort experience a DLT, then the dose de-escalation cohort -1 will accrue. This dose de-escalation cohort will be treated with 1 mg intratumoral SD-101 and 560 mg ibrutinib. If \leq 2 out of 6 subjects in the dose de-escalation cohort experience a DLT, then this dose will be considered the RP2D. If 3 or more subjects in the de-escalation cohort experience a DLT, the study will be stopped.

Table 1. Dose Escalation Plan

Cohort	Dose (mg)	Total Enrollment per Cohort	Dose Escalation Rules
-1	1 mg SD-101 560 mg ibrutinib	6	1 of 6 or 2 of 6 DLT, RP2D is established 3 of 6 DLT, trial is stopped
1	3 mg SD-101 560 mg ibrutinib	6-9	0 of 6 or 1 of 6 DLT, RP2D is established at this level 2 of 6 DLT, expand cohort to 9 subjects 2 of 9 DLT, RP2D is established at this level 3 of 6-9 DLT, decrease to dose level -1
Phase 2 Expansion	RP2D	15	If the incidence of study drug-related DLTs as defined previously equals or exceeds 33% of treated subjects at RP2D dose level 1, enrollment will be stopped for dose level 1, and enrollment of 15 subjects will begin at dose level -1. If the incidence of study drug-related DLTs equals or exceeds 33% of treated subjects at RP2D dose level -1, then the trial is stopped

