10.2.1 Relevant Subset

This outcome will be measured on any individual who has received at least one intratumoral injection of SD-101 at the recommended phase 2 dose level. This will include any subjects treated during the phase 1B portion who were treated at the recommended phase 2 dose level.

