10.3.1 Relevant Subset

This outcome will be measured on any individual who has received at least one intratumoral injection of SD-101 at the recommended phase 2 dose level. This will include any subjects treated during the phase 1B portion who were treated at the recommended phase 2 dose level.

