12.3.2 Sample size justification

The reported overall response rate with single-agent ibrutinib in a similar population of relapsed/refractory low-grade follicular lymphoma has been 30% (12 of 40 subjects) (12), and

we previously reported an ORR of 27% to intratumoral CpG (4 of 15 subjects) (50). We will therefore expect overall response rate of >57% (ie, a 27% improvement over ibrutinib alone).

This trial design will enroll a minimum of 21 subjects at the recommended phase 2 dose (a minimum of 6 subjects in phase 1b and 15 subjects in the phase 2 expansion). For a true response rate of 57%, this sample size will provide 83.6% power to detect a significantly improved (95% confidence interval) response rate as compared to the previously reported ORR of 30% with ibrutinib alone.

A total of 6 to 15 subjects will be enrolled in the phase 1B 6 x 3 dose de-escalation portion. An additional 15 subjects will be enrolled in the expanded phase 2 cohort.

If $\leq 1/6$ subjects experience a DLT at a dose of intratumoral SD-101 of 3 mg, we will proceed to the expansion phase. If $2/6$ subjects experience a DLT at 3 mg, then an additional 3 subjects will be enrolled in the same dosing cohort. If ≥ 3 of 6 to 9 subjects experience a DLT, then a dose de-escalation cohort -1 of 6 subjects will be opened.

The sample size of 15 subjects in the expanded phase 2 cohort (with resulting total number of 21 to 24 subjects at the RP2D in the combined 1b/2 phases) allows estimation of the response rate $+\/- 0.21$ with 90% confidence. The chance of obtaining three or fewer responses out of 15 is only 2.1% if the true response rate is 49%, with 49% ORR being a historical benchmark for response rate in this population.

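### Section 12.2.1 sets no SD-101 dose condition on the primary response population, in conflict with 10.2.1 and 12.3.2; this matters only if 3 mg is dropped

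*Combined protocol and SAP*

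**What the plan says.** - **12.2.1 Analysis Population.** The response-evaluable population starts from "all enrolled subjects who received at least one dose of study treatment (ibrutinib or SD-101" and adds only that disease was assessed at least once after baseline. It "will be used as the primary population for analyses based on overall response". No SD-101 dose level is mentioned.
- **10.2.1 Relevant Subset.** The phase 2 primary outcome is measured on "any individual who has received at least one intratumoral injection of SD-101 at the recommended phase 2 dose level". Sections 10.3.1 (progression-free survival) and 10.4.1 (immune response) use the same rule. From phase 1b all three admit "any subjects treated during the phase 1B portion who were treated at the recommended phase 2 dose level".
- **12.3.2 Sample size justification.** "This trial design will enroll a minimum of 21 subjects at the recommended phase 2 dose", and precision is discussed "with resulting total number of 21 to 24 subjects at the RP2D in the combined 1b/2 phases".
- **Synopsis and 4.1, phase 1b branch.** With 3 or more DLTs among 6 to 9 subjects at 3 mg, "dose de-escalation will occur with a new cohort of 6 subjects at a dose of 1 mg SD-101 and 560 mg ibrutinib". With at most 2 DLTs in those 6, 1 mg becomes the RP2D. Otherwise the trial stops.
- **4.1 and Table 1, expansion branch.** If DLT incidence "equals or exceeds 33% of treated subjects at RP2D dose level 1, enrollment will be stopped for dose level 1", and 15 subjects are then enrolled at 1 mg. Reaching 33% there as well stops the trial. Table 1 labels both levels RP2D.
- **6.1.** SD-101 is not reduced outside the design rules.

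**The concern.** Sections 12.2.1 and 10.2.1 define the set for the same primary outcome differently, and no text says which governs. The two agree on dose while 3 mg stays the RP2D. They part once 3 mg is rejected, because 12.2.1 then keeps the 6 to 9 subjects treated only at the rejected dose.

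The phase 2 result is meant to describe the dose carried forward. A pooled rate would describe a mixture of doses, and responses at 3 mg could lift a 1 mg dose that adds nothing past the 30% comparator. In an open-label trial the population should not be left to be chosen once responses are known.

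There is a second gap under the 33% rule. After a halt during the expansion, the plan does not say whether the earlier 3 mg subjects still count as treated at the RP2D. Only 15 subjects are then enrolled at 1 mg.

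**Working it through.** **Inputs.** Cohort sizes 6 to 9 (3 mg), 6 (1 mg) and 15 (expansion), with the DLT rules, come from 4.1. The null ORR of 30%, the alternative of 57%, n = 21 and 83.6% power come from 12.3.2. The documents give no DLT rate for the combination and no ORR by SD-101 dose, so those are assumed and varied. All subjects are taken as assessed.

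**1. The plan's own power.** One-sided 0.05, normal approximation:

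Power = Φ[(0.27·√n − 1.645·√(0.30 × 0.70)) / √(0.57 × 0.43)]

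At n = 21 this is Φ(0.977) = 83.6%, which reproduces 12.3.2.

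**2. Set sizes after a phase 1b rejection.**
- 10.2.1: 6 + 15 = 21, all at 1 mg.
- 12.2.1: 21 + 6 = 27 up to 21 + 9 = 30. Share never given the RP2D: 6/27 = 22% to 9/30 = 30%.

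**3. Probability of that path.** Phase 1b must reject 3 mg and cohort -1 must pass:

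{P(≥3 of 6) + P(2 of 6) × P(≥1 of 3)} × P(≤2 of 6 at 1 mg)

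At a 20% DLT rate, rejection is 0.0989 + 0.2458 × 0.488 = 0.219. Cohort -1 passes with probability 0.901 at the same rate, or 0.984 at half of it.

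| DLT rate at 3 mg | 3 mg rejected | Path, same rate at 1 mg | Path, half the rate at 1 mg |
|---|---|---|---|
| 10% | 4% | 4% | 4% |
| 20% | 22% | 20% | 22% |
| 30% | 47% | 35% | 45% |
| 40% | 70% | 38% | 63% |

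**4. Error in the reported 1 mg ORR on that path.** This is the off-dose share times (3 mg ORR − 1 mg ORR). With 30% at 1 mg and 57% at 3 mg it is 0.222 × 0.27 = +6 points to 0.30 × 0.27 = +8 points. It is zero if the ORRs are equal and negative if 1 mg is better.

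**5. Chance of wrongly excluding 30% on that path, with a true 1 mg ORR of 30%.** The smallest response counts whose exact two-sided 95% interval lies above 30% are 12 of 21, 14 of 27 and 15 of 30. The pooled count is the sum of two binomials.

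| True ORR at 3 mg | 10.2.1 set (21) | 12.2.1 set (27 to 30) |
|---|---|---|
| 30% | 0.9% | 1.4% to 1.7% |
| 40% | 0.9% | 2.6% to 3.9% |
| 50% | 0.9% | 4.5% to 7.8% |
| 57% | 0.9% | 6% to 12% |

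The first row shows that sample size alone explains little of the rise. With a one-sided 0.05 score test the 57% row reads 7% against 13% to 21%.

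**6. Over all trials, 57% row, 20% DLT rate.** 0.197 × 0.062 = 1.2%, up to 0.215 × 0.117 = 2.5%: about 1% to 3%.

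**7. After a 33% halt at 3 mg.** n = 15 at 1 mg. The formula in step 1 gives Φ(0.590) = 72%. The 90% half-width is 1.645 × 0.5/√15 = 0.21, the figure 12.3.2 already attaches to 15 subjects.

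**The case against.** The best defence is that the rest of the plan settles the dose question. Section 10.2.1 says whom the primary outcome is measured on and which phase 1b subjects count, two further sections repeat the rule, and 12.3.2 sizes on the RP2D. Section 12.2.1 stands under a phase 2 efficacy label and can be read as an evaluability filter on that set. This is probably what the sponsor intends. But the text does not say so, and 12.2.1 is the statistical definition an analyst would program. Nor does the label supply the condition: read as expansion subjects only, it gives 15, which contradicts both 10.2.1 and the 21 behind the power.

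The likelihood can also be disputed. Section 4.1 expects no added toxicity from the combination, and 5.1 reports no DLT at 1, 2 and 4 mg with radiation. Against that, 10.1.1 counts any drug-related Grade 3 or higher hematological toxicity in Days 1-30 as a DLT, and 5.2 reports 29% Grade 3 or 4 neutrophil decreases with ibrutinib alone in mantle cell lymphoma, over much longer exposure. The DLT rate is therefore open, which is why a range is shown.

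The 6 to 9 off-dose subjects are a maximum. DLT is a listed reason for withdrawal (4.11) and the first scheduled response imaging is at Week 12 (4.3.8), so some may never be assessed.

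**Conclusion.** The inconsistency is real and worth correcting, but conditional. If 3 mg is kept throughout, the dose clause changes nothing. If phase 1b rejects 3 mg and cohort -1 passes, 12.2.1 followed literally pools up to 22% to 30% off-dose subjects. The sizes above rest on assumed DLT and response rates.

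A reader might infer three stronger things that the documents do not support:
- *That the plan chose to pool doses.* Sections 10.2.1, 10.3.1, 10.4.1 and 12.3.2 all point the other way. This is a mismatch in wording.
- *That the chance of rejecting 3 mg (up to 70% at a 40% DLT rate) is the chance of the problem.* Under 4.1 the trial stops if cohort -1 fails, and there is then no phase 2 expansion to pool with. The path probability is 38% to 63% at that rate.
- *That the false-positive risk is 6% to 12%.* That holds only on this path, with no gain over 30% at 1 mg and the full 57% at 3 mg, which is close to a worst case. It is about 1% to 3% of all trials at a 20% DLT rate, and smaller for narrower gaps between doses.

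The shortfall after a 33% halt does not depend on how 12.2.1 is read: 15 subjects at 1 mg, with 72% power instead of 83.6%.

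**What to change.** - **12.2.1:** require at least one intratumoral SD-101 injection at the RP2D, in phase 1b or phase 2, so that the set matches 10.2.1. Report ORR for subjects treated at a rejected dose in a separate table. Whether a post-baseline assessment should be required is a different question, but the wording should be the same in both sections.
- **4.1 or 10.2.1:** state that after a 33% halt at 3 mg the RP2D is 1 mg and the 3 mg subjects are outside the primary set. State that if 1 mg also stops, ORR is reported by dose level with no RP2D claim.
- **12.3.2:** state that after a 33% halt the 1 mg set is 15 with 72% power by the plan's own formula. Its precision of +/- 0.21 is already given.

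The cost is a few sentences and one table. No patients or data are added.

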Hepatic Impairment: Ibrutinib is metabolized in the liver. In a hepatic impairment trial, a single dose of 140 mg of ibrutinib was administered in non-cancer subjects. Ibrutinib AUC increased 2.7-, 8.2- and 9.8-fold, respectively, in subjects with mild (n = 6), moderate (n = 10) and severe (n = 8) hepatic impairment relative to subjects with normal liver function. Ibrutinib Cmax increased 5.2-, 8.8- and 7.0-fold, respectively, in subjects with mild, moderate and severe hepatic impairment relative to subjects with normal liver function.

Drug Interactions

Coadministration of Ibrutinib with CYP3A Inhibitors: In a sequential design trial of 18 healthy, fasted volunteers, a single dose of 120 mg of ibrutinib was administered alone on Day 1 and a single dose of 40 mg of ibrutinib was administered on Day 7 in combination with 400 mg of ketoconazole (given daily on Days 4 to 9). Ketoconazole increased ibrutinib dose-normalized Cmax and AUC 29-fold and 24-fold, respectively. Simulations using fasted conditions indicate that moderate CYP3A inhibitors diltiazem and erythromycin may increase AUC of ibrutinib by 5- to 8-fold.

Coadministration of Ibrutinib with CYP3A Inducers: PK data from a dedicated drug interaction trial showed that rifampin (a strong CYP3A inducer) decreases ibrutinib Cmax and AUC by more than 13- and 10-fold. Simulations using PBPK suggested that a moderate CYP3A inducer (efavirenz) may decrease the AUC of ibrutinib by up to 3-fold.

Efficacy of Ibrutinib in Follicular Lymphoma

Ibrutinib has been studied in the treatment of subjects with low-grade follicular lymphoma. In a phase 1 study of subjects with relapsed or refractory B-cell malignancies, 13 subjects with follicular lymphoma were evaluated for response to ibrutinib, with 7/13 subjects showing a >50% decrease in sum of the largest diameter of each target lesion (11). The MTD in this study was 560 mg daily and this dose showed full-target occupancy. Preliminary results from a phase 2 trial of ibrutinib monotherapy in relapsed/refractory follicular lymphoma showed an overall response rate of 30% in 40 subjects on the intention-to-treat analysis. An additional 14 subjects had reduction of tumor size not meeting response criteria (12).

Efficacy of Ibrutinib in Marginal Zone Lymphoma

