Phase 2 (SD-101 dose Cohort Expansion): Once the safety profile and tolerability of all doses tested has been characterized and the RP2D of SD-101 has been defined during the dose de-escalation phase of this trial, the RP2D dose cohort will be expanded by an additional 15 subjects. This will enable further characterization of the immunoregulatory activity and preliminary antitumor effects of this treatment regimen. The treatment schema for SD-101, RT and ibrutinib will remain the same as previously described.

Clinical safety monitoring of subjects enrolled during this additional Cohort Expansion portion of the study will be the same as conducted during the dose escalation portion of the study (ie, part 1). If the chosen RP2D is dose level 1 (3 mg SD-101) and the combined incidence of study drug-related DLTs of any kind (ie, Grade 3 injection site reaction, hematologic or non-hematologic DLT) is equal to or exceeds 33% of treated subjects at any point during treatment, this will prompt a halt in enrollment at that dose level. Enrollment of 15 subjects will then begin at the lower dose level of 1 mg SD-101. If the incidence of DLTs in the lower dose cohort equals or exceeds 33%, the trial will be stopped.

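### The primary response rate has two denominators, and the one named primary drops treated subjects who were never assessed, while the 30% benchmark is intention-to-treat and the power counts all 21

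*Combined protocol and SAP*

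**What the plan says.** Two sections of the combined protocol and SAP define who counts towards the phase 2 primary outcome.

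- **Section 10.2.1 (Relevant Subset)** measures response on "any individual who has received at least one intratumoral injection of SD-101 at the recommended phase 2 dose level". Phase 1b subjects count if they were treated at that dose. No post-baseline assessment is required.
- **Section 12.2.1 (Analysis Population)** defines a response-evaluable set: enrolled subjects who "received at least one dose of study treatment (ibrutinib or SD-101) and provided at least one post-baseline response (or disease) assessment". It adds: "The response-evaluable population will be used as the primary population for analyses based on overall response". It has no dose-level restriction and does not define a disease assessment.

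The planned comparison is in Section 12.3.2. The benchmark is 30% with ibrutinib alone, which Section 2.2.2 reports as an "overall response rate of 30% in 40 subjects on the intention-to-treat analysis". On size, "This trial design will enroll a minimum of 21 subjects at the recommended phase 2 dose", and for a true rate of 57% "this sample size will provide 83.6% power to detect a significantly improved (95% confidence interval) response rate". The same section gives the total as "with resulting total number of 21 to 24 subjects at the RP2D in the combined 1b/2 phases".

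**The concern.** The two definitions differ on whether a treated subject without a post-baseline assessment stays in the denominator. Neither section refers to the other, and no scoring rule is given for such a subject.

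The direction is known. An unassessed subject cannot appear in the numerator as a documented responder, so removing that subject leaves the numerator alone and shrinks the denominator. The set named primary therefore leans upward whenever anyone is unassessed. It is then compared with a rate described as intention-to-treat, using a power figure that assumes all 21 subjects count. That comparison is the only powered claim in the plan. With the denominator open, it could be chosen after the results are known.

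A second gap is separate. Section 12.2.1 has no restriction to the recommended phase 2 dose. If that dose becomes 1 mg, its literal wording also admits the 6 to 9 phase 1b subjects treated at 3 mg. It would likewise admit any expansion subjects treated at 3 mg before a halt under Section 4.1, after which "Enrollment of 15 subjects will then begin at the lower dose level of 1 mg SD-101". This could move the rate either way. Sections 10.2.1 and 12.3.2 show that only subjects at the recommended dose were meant.

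**Working it through.** **Inputs.** From Sections 2.2.2 and 12.3.2: p0 = 0.30 (12 of 40), p1 = 0.57, N = 21 (6 + 15), upper total 24, stated power 83.6%. The number unassessed, m, is not given; I take m = 0 to 3 as an assumption. No phase 2 test is specified.

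**1. The plan's own power.** One-sample normal approximation, one-sided 5%:

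Power = Φ[(p1 − p0 − 1.645·√(p0(1−p0)/n)) / √(p1(1−p1)/n)]

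With n = 21: √(0.21/21) = 0.1000 and √(0.57·0.43/21) = 0.1080, so Φ[(0.27 − 0.1645)/0.1080] = 83.56%. This matches 83.6%. The two-sided 5% version gives 75.3%. With n = 20 the one-sided figure is 82.0%, so the stated power does count all 21.

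**2. Shift in the rate, no test involved.** If the all-treated rate is 30% and the m unassessed are non-responders, the rate among the assessed is 0.30·21/(21 − m): 31.5%, 33.2% and 35.0% for m = 1, 2, 3.

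**3. Chance of beating 30% when the all-treated rate is 30%.** Responders follow Binomial(N − m, 0.30·N/(N − m)). The 12.2.1 set uses denominator N − m. The 10.2.1 set uses N, with unassessed subjects scored as non-responders; that scoring rule is mine, because 10.2.1 states none. The score test passes if (x/n − 0.30)/√(0.21/n) ≥ 1.645. The exact test passes if the lower two-sided 95% Clopper–Pearson limit exceeds 30%.

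| N | Test | m | 12.2.1 set: cut-off, chance | 10.2.1 set: cut-off, chance |
|---|---|---|---|---|
| 21 | score | 1 | 10/20, 6.5% | 10/21, 6.5% |
| 21 | score | 2 | 9/19, 14.2% | 10/21, 6.3% |
| 21 | score | 3 | 9/18, 13.9% | 10/21, 6.0% |
| 21 | exact | 1 | 11/20, 2.5% | 12/21, 0.8% |
| 21 | exact | 2 | 11/19, 2.3% | 12/21, 0.7% |
| 21 | exact | 3 | 10/18, 6.0% | 12/21, 0.6% |
| 24 | score | 1 | 11/23, 7.2% | 11/24, 7.2% |
| 24 | score | 2 | 11/22, 7.0% | 11/24, 7.0% |
| 24 | score | 3 | 10/21, 14.5% | 11/24, 6.7% |
| 24 | exact | 1 | 12/23, 3.0% | 13/24, 1.1% |
| 24 | exact | 2 | 12/22, 2.8% | 13/24, 1.0% |
| 24 | exact | 3 | 12/21, 2.7% | 13/24, 0.9% |

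Part of each contrast is discreteness. To separate it, hold the 12.2.1 sample size and score cut-off fixed at N = 21 and change only the true rate among the assessed, from 30% to the shifted value in step 2. The chance then rises from 4.8% to 6.5%, 8.4% to 14.2%, and 6.0% to 13.9% for m = 1, 2, 3.

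**4. Single results that flip.**
- 11/21 has an exact lower limit of 29.8%, which does not exclude 30%; 11/20 has 31.5%, which does.
- Under the score test, 9/21 gives z = 1.286 (one-sided p = 0.099); 9/19 gives z = 1.652 (p = 0.049).

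**The case against.** Section 12.2.1 does name a primary population. One can read 10.2.1 as saying on whom the outcome is measured and 12.2.1 as saying who is analysed, which would leave only a missing cross-reference and a missing scoring rule. That reading does not settle the matter. Section 10.2.1 defines the subset for the same primary outcome, and the sample size counts subjects at the recommended dose as 10.2.1 does. Even if 12.2.1 governs, its set does not match the benchmark or the power.

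The stronger objection is size, and most of it stands:

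- Few subjects should be unassessed. Section 4.3.9 calls for final-visit imaging if none was done within 4 weeks, Section 4.11 says those procedures should be completed on early withdrawal, and entry requires a life expectancy above 4 months. A broad reading of disease assessment would also keep early progressors in. Against that, first response imaging is at Week 12, and Section 4.11 lists withdrawn consent and loss to follow-up, for which a final scan is not assured.
- The pass rates depend on the test. The score test shows no difference with one of 21 unassessed, or with one or two of 24. The 14.2% rests on 9/19 only just clearing 1.645. Under the exact limit, the 12.2.1 set stays within 2.5% for one or two of 21 unassessed, and much of the contrast is that the all-treated set is very conservative.
- How many of the 40 benchmark subjects were unassessed is not given, so the intention-to-treat mismatch cannot be sized.
- The rule in Section 12.4 (at least 6 responses) is a count, so dropping unassessed subjects does not change it.

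Keeping 12.2.1 primary, with a scoring rule and an all-treated sensitivity analysis, would also remove the conflict. It would leave the primary comparison leaning upward against an intention-to-treat rate.

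**Conclusion.** The concern holds. Two stated rules for the primary denominator conflict, and the one named primary can bias the response rate only upward against the benchmark. The shift is about 1.5, 3.2 or 5.0 percentage points with 1, 2 or 3 of 21 unassessed. The chance of wrongly beating 30% ranges from unchanged to roughly doubled under the score test that reproduces the stated power, and is several times higher, from a low base, under an exact limit.

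These figures assume 0 to 3 unassessed subjects, all scored as non-responders, and a test that the plan does not name. With nobody unassessed and a 3 mg recommended dose, the two sets coincide and there is no effect. The missing dose restriction matters only if the recommended dose becomes 1 mg. This should be corrected, but it is probably small in practice; confidence is medium.

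**What to change.** In Section 12.2.1:

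1. Make the Section 10.2.1 set (at least one SD-101 injection at the recommended phase 2 dose) the primary population for response rate.
2. Count subjects with no post-baseline assessment as non-responders.
3. Report the response-evaluable rate as a sensitivity analysis, restricted to the recommended dose and with disease assessment defined.
4. State the number unassessed beside both rates.

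A minor related point: Section 4.3.8 scores response by reference 49 and leaves out the draining nodes of the injected region, while Section 10.2.2 uses the Lugano classification (reference 51) without that exclusion. Reconcile them so that one criterion applies and the handling of draining nodes is clear.

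The cost is wording only, with no new data or visits. The reported rate may be slightly lower, and power falls if 57% holds only among assessed subjects. Using the formula in step 1 with n = 21 and p1 = 0.57·(21 − m)/21, power is 76.5%, 68.1% or 58.7% for m = 1, 2, 3. The response-evaluable set (n = 20, 19, 18 at 57%) would give 82.0%, 80.4% or 78.6%.
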